### 3 STUDY ENDPOINTS

#### 3.1 Efficacy Endpoints

COVID-HIGIV is indicated for the treatment and prevention of COVID-19. This study is conducted in healthy adult volunteers to evaluate the safety and pharmacokinetics of COVID-HIGIV. Efficacy is not evaluated in this study.

#### 3.2 Safety Endpoints

The following primary safety endpoints will be evaluated:

- Adverse Events (AEs) within 72 hours post-dosing.
- AEs leading to discontinuation or temporary suspension of infusion.
- AEs and Serious Adverse Events (SAEs) up to 84 days post-administration of a single COVID-HIGIV dose.

#### 3.3 Pharmacodynamics Endpoints

**Primary PK Endpoints:** The following PK parameters will be estimated after a single dose of COVID-HIGIV infusion:

- $AUC_{0-\text{last}}$ : area under the concentration-time curve from time 0 to the last quantifiable concentration after a single dose. Time 0 is defined as the end of infusion; time  $t$  is defined as time of the last quantifiable concentration.
- $AUC_{0-\text{inf}}$ :  $AUC_{0-\text{last}}$  plus the additional area extrapolated to infinity.
- $AUC_{0-14d}$ : AUC from time 0 to 14 days post-dosing.
- $AUC_{0-28d}$ : AUC from time 0 to 28 days post-dosing.
- $C_{\text{max}}$ : maximum observed post-dosing concentration.
- $T_{\text{max}}$ : time at which  $C_{\text{max}}$  occurs.
- $C_{\text{min28d}}$ : observed or estimated concentration (by interpolation/extrapolation) at 28 days post-dosing.
- $\lambda_z$ : terminal elimination rate constant after a single dose.
- $T_{1/2}$ : apparent terminal elimination half-life after a single dose.
- $CL$ : systemic clearance after a single dose.
- $V_z$ : volume of distribution after a single dose.

**Secondary PK Endpoints:** following body weight normalized PK parameters will be estimated as PK parameter divided by subject body weight (kg) at baseline.

- $C_{\text{max}}\text{BWN}$ : Body weight normalized  $C_{\text{max}}$
- $C_{\text{min28d}}\text{BWN}$ : Body weight normalized  $C_{\text{min28d}}$

[COVID-HIGIV]  
[EBS-CVH-003]

- $AUC_{0-14d}BWN$ : Body weight normalized  $AUC_{0-14d}$
- $AUC_{0-28d}BWN$ : Body weight normalized  $AUC_{0-28d}$
- $AUC_{0-last}BWN$ : Body weight normalized  $AUC_{0-last}$
- $AUC_{0-inf}BWN$ : Body weight normalized  $AUC_{0-inf}$

### 3.4 Exploratory Endpoints

There are no exploratory endpoints in this study.

## 4 POWER AND SAMPLE SIZE CONSIDERATIONS

There was no formal sample size calculation for this Phase 1 study. However, the number of subjects planned to receive COVID-HIGIV is deemed sufficient to descriptively assess safety and PK of three COVID-HIGIV dose levels with healthy adults.

In total, 28 subjects are planned for the study. Eight subjects for each of the three COVID-HIGIV dose levels, and four subjects for placebo arm.

## 5 DATA CONSIDERATIONS

### 5.1 Protocol Deviations

A protocol deviation is any change, divergence, or departure from the study design or procedures defined in the protocol. The occurrence of protocol deviations will be routinely monitored for evaluation of Investigator compliance with the protocol, GCP, and regulatory requirements.

Upon identification, protocol deviations will be classified by category, sub-category and type (important/not important) per the Protocol Deviation Management Plan (PDMP *version 2.0 19May2021*). All protocol deviations will be reviewed, finalized and documented prior to final database lock and study unblinding.

Protocol deviations due to the COVID-19 pandemic will be recorded and indicated.

#### 5.1.1 Important Deviations

Emergent will review all protocol deviations on an ongoing basis and will determine if the deviation should be categorized as an Important Protocol Deviation, which are a subset of protocol deviations that might significantly affect the completeness, accuracy, and/or reliability of the study data or that might significantly affect a subject's rights, safety, or well-being. For example, important protocol deviations might include enrolling subjects in violation of key eligibility criteria designed to ensure a specific subject population or failing to collect data necessary to interpret primary endpoints.

Examples of major protocol deviations may include:

- Subjects who were enrolled/randomized but did not meet study eligibility criteria.

[COVID-HIGIV]  
[EBS-CVH-003]

- Subjects who met criteria for study termination but remained in the study.
- Subjects who received the wrong treatment (IP or dosage level).
- Other deviations from key study procedures such as accidental unblinding, subject noncompliance with treatment schedule, subject noncompliance with assessment of primary outcome measures.

The importance of a protocol deviation will be assessed and determined case by case by study team review.

### **5.1.2 Reporting of Protocol Deviations**

The important protocol deviations will be summarized by category and treatment arms. Listings of important and non-important protocol deviations will be provided respectively.

### **5.2 Analysis Sets**

- Safety Set (SS): all randomized subjects who receive any amount of COVID-HIGIV or placebo. Analyses based on SS will be analyzed according to the study treatment arm (dispensed IP and dosage level) recorded in Drug Accountability form.
- PK Set (PKS): all subjects who are randomized and received COVID-HIGIV according to the protocol, had adequate data for calculation of PK parameters, and had no protocol deviations that would affect PK assessment.

### **5.3 Analysis Groups**

Safety evaluations will be based on Safety Set, subjects will be grouped by the study treatment they received (dispensed IP and dose level). PK evaluation will be based on PK Set; subjects who receive placebo only will be excluded.

### **5.4 Analysis Time Points**

Study visits occur on protocol-specified days are associated with visit windows (see details in [Appendix I: Schedules of Events](#)). For purposes of data analysis, if the study day of assessment falls within the visit window, the corresponding analysis visit will be assigned as specified as following:

- Screening: 7 days prior to randomization.
- Day 1 - Randomization (the randomization day is defined as Day 1 of the study)
- Day 1 - Dosing (dosing is scheduled on the same day as randomization):
  - PK sampling nominal timepoints on Day 1:
    - Pre-dose: 0-4 hours
    - Post-dose: 1, 2, 4, 8, 12 hours
  - Vital Signs nominal timepoints on Day 1:

[COVID-HIGIV]  
[EBS-CVH-003]

Pre-dose: 0-2 hours

Post-dosing: 30 and 60 minutes.

- Day 2 (discharge): 24 hr after end of IV infusion on Day 1
- Day 4 (3 days post-dose), Day 8 (7 days post-dose), Day 15 (14 days post-dose), Day 22 (21 days post-dose), Day 29 (28 days post-dose), 43 (42 days post-dose), and 57 (56 days post-dose)
- Day 85 (84 days post-dose, end of study) / Early Withdrawal

For all analyses, pre-dose is defined as prior to the start of infusion. Post-dose timepoints in unit of hour are defined as post the infusion stop time; unless otherwise specified; the post-dose timepoints in unit of day are defined as post the day of infusion, which starts and ends on the same day in this study.

Data at unscheduled visits/timepoints that do not fall into a scheduled visit or nominal timepoint window will not be presented in the summary analyses by visit/timepoint but will be included in the summary tables by maximum toxicity grade or abnormality when applicable, and in data listings.

## 5.5 Definition of Baseline

For all analyses, the baseline value for each measure is defined as the last non-missing value prior to the dosing of any study treatment (COVID-HIGIV or placebo).

## 5.6 Multiple Records in an Analysis Window

For clinical laboratory data, vital signs, and physical examinations, if multiple valid non-missing observations exist in an analysis window for a specific visit, a single value will be chosen in the by-visit summary analyses based on the following rules:

- if the analysis values are pre-dosing, the latest pre-dose value will be selected as baseline;
- if the analysis values are numeric and the toxicity grades are available, the record with the highest toxicity grade will be selected;
- if the analysis values are numeric and the toxicity grades are identical or not available, the last (newest) value will be used;
- if the analysis values are categorical, the most conservative value will be selected (e.g., abnormal will be selected over normal).

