## **9.4 Clinical Laboratory Tests**

### **9.4.1 Safety Laboratory Tests**

Clinical safety laboratory assessment includes the following –

- Chemistry panel: sodium ( $\text{Na}^+$ ), potassium ( $\text{K}^+$ ), chloride ( $\text{Cl}^-$ ), bicarbonate ( $\text{HCO}_3^-$ ), blood urea nitrogen (BUN), creatinine, glucose, total and direct bilirubin, alanine

[COVID-HIGIV]  
[EBS-CVH-003]

aminotransferase (ALT), aspartate aminotransferase (AST), and lactate dehydrogenase (LDH),

- Hematology panel: complete blood count (CBC); i.e., red blood cells, white blood cells, platelets, hemoglobin, and hematocrit, with differential (neutrophils, eosinophils, basophils, monocytes and lymphocytes).
- Urinalysis: PH, specific gravity, urobilinogen, blood, bilirubin, color, glucose, ketone, leukocyte esterase, nitrite, protein.

Numeric laboratory results and change from baseline will be summarized by analysis group at scheduled visits only.

The abnormality of the laboratory results (Low, Normal, High) will be assessed according to normal ranges. The clinical significance of abnormality will be assessed by PI. Laboratory results will be graded with severity grade 1 to 4 (grade 1=mild, through grade 4=potentially life-threatening) according to the DAIDS Table for Grading the Severity of Adult and Pediatric Adverse Events ([Appendix II](#)).

Values not meeting criteria for toxicity of at least grade 1 will be considered as grade 0. If laboratory tests with toxicity criteria for both increased and decreased directions exist (e.g., Sodium), toxicity grades for each direction will be presented separately (e.g., Sodium Increased versus Sodium Decreased).

For selected laboratory parameters, shift of abnormality (Low, Normal, High) and toxicity grade from baseline to the maximum/minimum post-dosing results will be tabulated with counts and percentages by analysis group and timepoint.

The qualitative results of urinalyses will be summarized by analysis group at scheduled visits. Count and percentage of subjects of each result category will be presented.

All laboratory records will be provided in the subject data listings, with applicable toxicity grades or abnormal flags displayed. A separate listing will be provided for post-baseline laboratory results at Grade 1 or higher.

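### SAP 5.6 picks the latest record before dosing but the highest-grade record after it, so mean change from baseline in laboratory tests and vital signs is biased away from normal when one window holds records of different grades

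*SAP*

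**What the plan says.** SAP 5.6 covers laboratory data, vital signs and physical examinations. When a window holds several valid records, "a single value will be chosen in the by-visit summary analyses based on the following rules". The rules that matter here are:

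- Before dosing: "if the analysis values are pre-dosing, the latest pre-dose value will be selected as baseline". SAP 5.5 agrees: "the baseline value for each measure is defined as the last non-missing value prior to the dosing of any study treatment".
- After dosing, graded numeric values: "if the analysis values are numeric and the toxicity grades are available, the record with the highest toxicity grade will be selected".
- After dosing, no difference in grade: "if the analysis values are numeric and the toxicity grades are identical or not available, the last (newest) value will be used".

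The chosen values go into numeric summaries. For laboratory tests, SAP 9.4.1 says: "Numeric laboratory results and change from baseline will be summarized by analysis group at scheduled visits only". SAP 9.5.1 summarises vital signs and their change from baseline by time point, without the restriction to scheduled visits. SAP 6.1 makes these summaries means, SDs, medians and ranges.

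SAP 5.4 keeps unscheduled data out of the by-visit summaries only when they fall outside every window. Such data "will be included in the summary tables by maximum toxicity grade or abnormality when applicable". Nothing in the SAP gives numeric means a different selection rule from grade or shift tables.

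**The concern.** Change from baseline is a difference of two selected values. If both are selected in the same way, any distortion from the selection cancels on average. Here an abnormal pre-dose value that settles on repeat is replaced by the repeat, while an abnormal post-dose value that settles on repeat is kept. A subject with the same readings before and after dosing can therefore show a change.

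In-window repeats are foreseeable. Protocol 6.3.5 allows safety laboratory tests and vital signs at unscheduled visits. Day 2 and Day 4 are the only post-dose visits with routine laboratory tests, and Protocol 9.3.1 lists laboratory tests and vital signs among the assessments used to evaluate the primary safety endpoints. With arms of 8, 8, 8 and 4, one retested subject is visible in a mean. What is at stake is the reading of the descriptive mean-change tables, not a test or an error rate.

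**Working it through.** **Inputs from the documents.** The selection rules are in SAP 5.5 and 5.6, the vital-sign grades in SAP Appendix III and the arm sizes 8/8/8/4 in SAP 4. The plan gives no figure on this point, so there is none to reproduce. **Assumed:** parameter means, between- and within-subject SDs, and when repeats are taken.

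**Step 1: form of the bias.** Let T be a subject's unchanged true level, b the selected baseline and p the selected post-dose value. Spurious mean change = E(p − T) − E(b − T). With one rule on both sides the two terms are equal and the difference is zero. SAP 5.6 makes them unequal.

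**Step 2: one subject, assumed systolic readings.** Suppose the readings are 152 (grade 2) then 132 (grade 0) in the pre-dose window, and the same pair in a post-dose window.

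- SAP rule: 152 − 132 = +20.
- Scheduled (first) record on both sides: 152 − 152 = 0.
- Latest record on both sides: 132 − 132 = 0.

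This moves an active-arm mean by 20/8 = 2.5 mmHg, or the placebo mean by 20/4 = 5.0 mmHg.

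**Step 3: simulation with zero true change.** Each scenario had 1,000,000 subjects and up to two exchangeable records per window, graded by Appendix III. Change is under the SAP rule; the last column divides the triggered-repeat change by the within-subject SD.

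| Parameter (mean / between SD / within SD) | Repeat only after grade ≥1 | Two records always | Within-SD units |
|---|---|---|---|
| Systolic BP 120/10/6, mmHg | +0.24 | +0.23 | 0.24/6 = 0.04 |
| Systolic BP 120/10/10 | +0.76 | +0.75 | 0.76/10 = 0.08 |
| Systolic BP 130/10/8 | +1.64 | +1.64 | 1.64/8 = 0.21 |
| Heart rate 70/9/6, beats/min | −0.53 | −0.51 | 0.53/6 = 0.09 |
| Heart rate 65/9/6 | −0.99 | −0.99 | 0.99/6 = 0.17 |
| Respiratory rate 15/1.5/1.5, breaths/min | +0.34 | +0.34 | 0.34/1.5 = 0.23 |
| Respiratory rate 16/1.5/1.5 | +0.45 | +0.44 | 0.45/1.5 = 0.30 |

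The sign follows whichever abnormal limit lies nearer the assumed mean, which is why heart rate moves down.

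**Step 4: which side causes it.** The two repeat patterns give nearly the same total for different reasons.

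- *Repeats only after an abnormal value.* After dosing, a normal first reading stands and an abnormal one is usually kept, so the selected value is close to the first reading, which is unbiased: E(p − T) is only about 0.002 to 0.03 within-subject SD. At baseline, abnormal first readings are replaced by repeats that regress toward T while normal first readings stay, so the baseline mean is pulled toward normal. This accounts for about 83–97% of the total.
- *Two records regardless of result.* The latest baseline record is unbiased. The whole shift, about 0.04 to 0.30 within-subject SD, comes from the post-dose highest-grade rule.

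**Step 5: same rule on both sides.** Latest/latest and highest-grade/highest-grade both gave a mean change within 0.02 of zero in every scenario. The scheduled record on both sides also gave zero within simulation error.

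**The case against.** The strongest reply has five parts.

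1. *Keeping an abnormal post-dose value is not in itself the fault.* A reader might infer that the mean is inflated because the settled repeat is discarded. When the repeat was ordered because the scheduled value was abnormal, the scheduled value is the one SAP 5.6 keeps, and a scheduled-record rule would keep it too. Step 4 bears this out. The stronger reading fails for triggered repeats; what stands is the mismatch with baseline.
2. *The rule does not take the higher reading.* A reader might apply the expected maximum of two independent readings, 1/√π = 0.56 within-subject SD. SAP 5.6 selects on grade and falls back to the newest record when grades tie, so two grade 0 readings add nothing. The simulated effect is well below 0.56.
3. *Baseline repeats are limited by design.* Vital signs have a scheduled reading within 2 hours before dosing (Protocol Table 1), which is normally the last one. Laboratory tests have only the Screening draw, and exclusion criterion 2 bars several analytes above the upper limit of normal. This stands and reduces how often the baseline mechanism can act.
4. *Early windows are narrow.* Day 2 is 24 ± 2 hours, Day 4 is 3 days ± 12 hours, and the post-infusion vital signs are ± 5 and ± 10 minutes. Many repeats would fall outside. The restriction in SAP 9.4.1 may also exclude unscheduled laboratory repeats, although SAP 5.4 and 5.6 read as admitting those in a window. This limits the size and leaves an ambiguity to settle.
5. *A worst-value rule is conservative.* That suits detection tables. The laboratory shift tables in SAP 9.4.1 already use post-dose extremes, and SAP 5.4 sends out-of-window data to the maximum-grade tables. In a mean table the rule is not reliably conservative: a high reading kept in the 4-subject placebo arm moves its mean twice as far as the same reading in an active arm and can mask a change there.

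**Conclusion.** The point holds as a mismatch of rules. That the bias exists, and that it runs away from normal, follows from SAP 5.5 and 5.6. Its size does not: 0.04 to 0.30 within-subject SD rests on assumed means, SDs and repeat patterns. The larger values arise where the assumed mean lies near a grade limit.

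The effect needs valid records of differing grade in one window, and the documents do not say how often that will happen. For parameters graded in both directions the shifts may partly cancel in the mean while widening the spread.

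A reader might infer that the safety conclusions or the comparison of arms are compromised. The documents do not support that. The primary safety endpoints are adverse events (SAP 3.2), no hypothesis is tested (SAP 6.4), and the rule is the same in every arm, so contrasts between arms are distorted on average only if abnormality or retest rates differ. This is a minor, worthwhile correction to descriptive tables.

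**What to change.** - **SAP 5.6:** for numeric by-visit summaries and change from baseline, use the scheduled record, or the valid record closest to nominal time, both before and after dosing. Keep highest-grade selection for the shift, maximum-grade and abnormality tables.
- **SAP 5.5:** add a sentence giving the matching baseline definition for these numeric tables. Without it the main source of bias under triggered repeats remains.
- **SAP 9.4.1:** state whether the restriction to scheduled visits excludes unscheduled repeats that fall inside a window.

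The cost is a few sentences across three sections and a record-selection flag in the programming. Mean tables may look slightly less conservative, but worst values remain in the grade and shift tables and in the listings.

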## 5.7 Coding Dictionaries

Medical history (including procedure history) and adverse events will be coded to system organ class and preferred terms using the Medical Dictionary for Regulatory Activities (MedDRA) dictionary version 23.0.

[COVID-HIGIV]  
[EBS-CVH-003]

Prior and concomitant medications will be coded to up to ATC Level 4 using WHO-DD version 2020-09-01.

## 5.8 Toxicity and Severity Grading

The toxicity and severity grading scales used for adverse events and clinical laboratory assessment in this study are provided in [Appendix II](#). Severity grading scales used for vital signs in this study are provided in [Appendix III](#).

Grade 1 = Mild, Grade 2 = Moderate, Grade 3 = Severe, Grade 4 = Potentially life-threatening. Event causes death will be assigned as Grade 5. Grade 0 is used to represent “normal” or “symptom not present”.

The severity of AEs, vital signs will be assessed by the principal investigator (PI) or the designee. For symptoms not appearing on the grading scale, the grading for generic “illness or clinical AE” will be used. Clinical laboratory results will be graded by the laboratory for analytes appearing in [Section 9.4](#), reviewed by the PI or the designee.

COVID-19 symptoms will be graded by Severity ([Appendix IV](#)) and Modified WHO Ordinal Scale ([Appendix V](#)).

## 6 STATISTICAL CONSIDERATIONS

### 6.1 General Considerations

Data summaries will be tabulated by appropriate grouping for each analysis population as specified in [Section 5.3](#).

Continuous endpoints will be summarized by descriptive statistics including number of non-missing observations (n), mean, standard deviation (SD), median, minimum, and maximum. When log-normal distribution is appropriate, logarithm transformation will be used and geometric mean (Geo. Mean) and geometric coefficient of variation as a percentage (Geo. CV%) will be reported. Categorical variables will be summarized by counts (n) and percentages of subjects (%) in each category, including missing or unknown when appropriate.

Unless otherwise specified, confidence intervals (CIs) are two-sided at 95% confidence level.

All derivations, statistical analyses, summaries, and listings will be generated using SAS Version 9.4 or higher (SAS Institute, Inc., Cary, North Carolina, United States).

### 6.2 Units and Precision

All clinical laboratory data and vital sign data will be reported using US convention units. Measures with non-standard units include:

- Anti-SARS-CoV-2 IgG Binding Titer: AU/mL, binding antibody titers normalized to reference standard ([Appendix VI](#)).

[COVID-HIGIV]  
[EBS-CVH-003]

- Anti-SARS-CoV-2 Pseudo-virus Neutralizing Antibody Titer: AU/mL, neutralizing antibody titers normalized to reference standard ([Appendix VI](#)).
- All PK concentrations will be reported in listings and analyzed with the same precision (with 1 decimal place) as the source data provided by the bio-analytical laboratory, unless otherwise specified. For derived PK parameters, the following convention will be used:
  - Elapsed time from dosing will be expressed as hours or days in the calculations and rounded to two decimal places.
  - Parameters derived directly from source data (e.g., Cmax, Tmax, minimum, maximum) or first-order statistics (e.g., mean) will be reported and analyzed with the same precision as the source data.
  - Second-order statistics (e.g., SD) will be reported with one more significant digit than the source data.
  - Percentages (including Geo. CV%) will be reported to one decimal place.
  - Ratios of means for PK parameters will be presented with two decimal places.

### 6.3 Derived Variables

This section provides definitions of the derived variables. In some cases, the definitions are provided in the relevant sections.

**Study Day 1** (SD1) is defined as the day of randomization. The day prior to Study Day 1 is Day -1. There is no Day 0.

Study day relative to SD1 will be calculated as:

**Study Day** = (assessment date – date of SD1 + 1) if the assessment is on or after SD1.

**Study Day** = (assessment date – date of SD1) if the assessment is before SD1.

Duration between event A and event B = (date/time of event B – date/time of event A).

For conversion of duration, 1 year = 365.25 days, 1 month = 365.25/12 = 30.4375 days.

